
Study Objectives:
 
 • Primary: • Secondary: 	
The primary objective is to ascertain if addition of Saxagliptin improves endothelial dysfunction in early type 2 diabetes patients.
 
The secondary objective is to establish CD34+ cell number, function and gene expression as important bio-markers to monitor endothelial function.

Study Design:
	
Prospective, double-masked, randomized placebo-controlled trial

Accrual Goal: (Total number of subjects)	N=42
Accrual Rate: (Number of subjects expected per month)	Recruit 42 patients in approximately 36 months.
Estimated: FPFV: LPFV: Follow Up: (dd-mm-yy)	FPFV: 01-10-12. LPFV: 01-06-15
Correlative Studies: (PK/PD, etc.)	N/A
Inclusion Criteria:	
 1. Adults aged 40-70 years. 2. Diagnosis of type 2 diabetes within the previous 8 years using criteria of the American Diabetes Association 3. Currently treated with no hypoglycemic agents other than a stable dose (>3 months) of metformin (≥ 1.0 to ≤ 2 grams daily). 4. HbA1C between 6 to 9% (both inclusive) 5. BMI 25 to 39.9 kg/m² (both inclusive)

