2 STUDY OBJECTIVES

2.1 Primary Objective

To investigate the effect of saxagliptin and lifestyle modification (diet and aerobic exercise intervention) separately on Endothelial function in patients whose HbA1C is between 6 to 9% (both inclusive) despite treatment with metformin (≥ 1.0 to ≤ 2 gm/d), stable dose for at least 3 months)

Cellular markers^{5-7,30}. We will use patient's peripheral blood derived CD34+ cells looking at number, function and gene expression changes pre and post saxagliptin.

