Week -4: Subjects will be screened and eligibility will be verified based on physical and laboratory tests. We will aim to recruit equal numbers of male and female patients will be recruited. All patients will be educated on the recommended lifestyle changes of maintaining a level of aerobic activity of 150 minutes/ week (non-supervised) and ideally receive dietary advice from the research coordinator, a diabetes educator, or a registered

dietitian (as per American Diabetes Association clinical guidelines²) specifically geared towards type 2 diabetes patients. We plan to monitor activity using accelerometers. We will allow 4 weeks for the patients to reach a steady state while implementing life style (diet and exercise) changes.

Week 0: At this stage patients will be randomized into the study. Subjects will have the first set of measurements. We will make sure that patients still meet the inclusion criteria. They will be started on medication or placebo and will be encouraged to continue 150 minutes/week of moderate physical exercise and dietary management for the remainder of the study.

Weeks 0, 6 and 12: Subjects will all have the same measurements and will continue on study medication or placebo. All primary and secondary measures as outlined before will be carried out.

- Primary Measures: CD34+ cell number, function and gene expression.
- Mononuclear cell population (day 0 of harvest) will be analyzed by FACS to obtain cell counts of different endothelial precursor lineage cells. Combinations of following cell markers will be used, such as CD34, KDR(VEGFR2), CD31, CD144 (VE-Cadherin), CD133 (a progenitor cell marker of indeterminate lineage) and CXCR4 (SDF1 α receptor)^{5,6,8,10,20,21,59}

For:

- CD34/KDR+
- CD34/ CXCR4+
- CXCR4 + CD31
- KDR + CD34
- Some of the MNC population will be put through a human CD34 magnetic bead column using Miltenyi Biotech Column to obtain CD34+ and CD34- cells. The CD34+ cells will be used for
- Colony Forming Unit Assay (CFU Assay) from mononuclear cell population (prior to magnetic bead sorting)
- Migration assay in response to SDF-1 (0, 10, 100 ng/mL) and if sufficient cells are available we will note migration in response to SDF1 (0, 10, 100 ng/mL)

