- Gene expression assays: Genes analyzed will be eNOS, PECAM-1, IGF-1, VEGF-alpha, VEGFR2, SDF-1, CXCR4 (receptor for SDF1), anti-oxidants MnSOD, Catalase, Cu-Zn SOD, Glutathione Peroxidase, extracellular SOD, pro-inflammatory markers such as IL6, TNF-alpha and Endothelin-1 genes and apoptosis cascade genes such as p53, p21, Bcl-2, GPX, Caspase-3 will be analyzed.

Secondary Measures:

- Highly selective C-reactive protein (hs-CRP), IL-6, TNF-alpha, Leptin ^{,18, 28}, and fasting lipid profile
- Serum SOD activity and SDF1 alpha (ELISA), VEGF-A (ELISA) and GLP-1 (ELISA) levels will also be assessed^{14,20,24,39}.
- Assessment of insulin sensitivity using the HOMA-IR³², calculated from individual serum measures (fasting glucose (mg/dl)* insulin (μU/mL)/405) ³⁷.
- Adiposity will be measured using the Tanita Body Composition Analyzer scale, measured as percentage body fat, BMI, waist-hip ratio^{5,55}
- Fasting lipid profile will be checked as a marker of insulin resistance and lipo-toxicity at weeks 0, 6, and 12⁵.
- We also intend to acquire Pulse wave analysis and Vascular Flow using SphygmoCor CP system from ATCOR to measure central arterial pressure and arterial stiffness^{38,42}. The secondary measures are indirect measures of endothelial inflammation in early type 2 diabetes patients. ^{30, 31, 32, 55, 56, 57}.
- Urine pregnancy testing for women of child bearing potential

We will obtain a total of 85mL of peripheral blood per visit. Of these 85 mL, 60 mL will be used to obtain CD34+ cells from MNC population and 25 mL for biochemistry and serum ELISA assays.

Methodology of Cellular Measure of Endothelial Function:

This is the strongest and most direct endothelial functional parameter, yet the least explored.

Here we plan to measure stem cell precursors of endothelium in subjects with type 2 diabetes as a bio-marker of endothelial health.

Day 0: FACS Analysis for CD34/CD31/KDR/CD133/CD144+, CXCR4 cells (note percentage)

Sort MNC for CD34+ cells for Migration, Tube Formation Assay (Functional Assay)

And gene expression assays.

Functional Assay (Cellular): At Day 0, post cell sorting for CD34 + cells we will note functional assays of these cells.

[figure not shown]
We plan to look at:

- Colony Forming Unit Assay
- Migration assay in response to SDF-1 and VEGF-A.

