Colony Forming Unit Assay: MNC's (prior to CD34 magnetic bead sorting) will be plated in Human Fibronectin Coated 6 well (5 million) or 12 well plates (2 million) from BD Biosciences or Millipore. Number of CFU will be determined at Day 5, post plating.

Migration property of the patient's CD34+ cells in response to SDF-1 will be assessed immediately post cell sorting on day 0 using modified Boyden chamber. Briefly, CD34+ cells (1-2x10e5) will be placed in the upper compartment, as shown below. Concentrations tested will be SADF-1 at concentrations of 0, 10, 100 ng/ml and if sufficient cells remain, VEGF-A at concentrations of 0, 20, 50 ng/mL^{12,34} dissolved in basal endothelial culture media. Other than this protocol one can also use Migration Assay kit using 3micron pore size from Cell BioLabs Inc. (catalog # CBA-103).

These tests will evaluate the functional (migration) property of CD34+ endothelial progenitor cells⁶⁰.

The CD34+ cells obtained at day 0 from peripheral blood derived mononuclear cell population will be analyzed for mRNA expression of various endothelial function related genes,

- The gene expression changes should indicate changes in paracrine properties of CD34+ cells pre and post saxagliptin therapy,
- Genes analyzed will be eNOS, and PECAM-1, VEGF, VEGFR2, SDF-1alpha, CXCR4, IGF-1^{36,42,43}. Intra-cellular antioxidant genes such as MnSOD, Catalase and GPX will also be noted^{22,23,44,45}. eNOS is a critical gene regulating EPC's nitric oxide production capability²². PECAM-1 is platelet endothelial cell adhesion molecule and indicates inflammatory potential of endothelial lineage cells. VEGF and IGF-1 are growth factors produced by healthy EPCs. MnSOD and Catalase are anti-oxidants which may be important endothelial anti-inflammatory agents and may promote healing in hyperglycemic conditions^{9,12,31,46}. Pro-inflammatory markers such as IL6, TNF-alpha and Endothelin-1 genes and apoptosis cascade genes such as p53, p21, Bcl-2, will be analyzed in addition to other genes previously mentioned.

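### The plan names no single primary outcome and no success rule: an open-ended panel of roughly 24 to 28 CD34+ outcomes is primary at one unsplit 0.05

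*Combined protocol and SAP*

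**What the plan says.** **What is primary.** Section 2.1 (Primary Objective) refers to "peripheral blood derived CD34+ cells looking at number, function and gene expression changes pre and post saxagliptin". The visit description in Section 6 lists "Primary Measures: CD34+ cell number, function and gene expression". The synopsis words its primary objective as an effect on endothelial dysfunction and names no measure for it. The CD34+ measures appear there only in the next line: "The secondary objective is to establish CD34+ cell number, function and gene expression as important bio-markers to monitor endothelial function".

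**What the three domains contain (Section 6).**
- Number: "Combinations of following cell markers will be used, such as CD34, KDR(VEGFR2), CD31, CD144 (VE-Cadherin", followed by four listed marker combinations, of which CD34 with KDR appears twice.
- Function: a colony-forming assay and migration towards SDF-1, and also "if sufficient cells remain, VEGF-A at concentrations of 0, 20, 50 ng/mL". The methodology text adds a further assay: "Sort MNC for CD34+ cells for Migration, Tube Formation Assay (Functional Assay".
- Gene expression: "Genes analyzed will be eNOS, PECAM-1, IGF-1, VEGF-alpha, VEGFR2, SDF-1, CXCR4 (receptor for SDF1), anti-oxidants MnSOD, Catalase, Cu-Zn SOD", and the list continues. A later paragraph repeats part of it and adds that "apoptosis cascade genes such as p53, p21, Bcl-2, will be analyzed in addition to other genes previously mentioned".

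**How it is tested.** The synopsis (Statistics) sets significance at p below 0.05, with no split and no statement of one or two sides. Section 8 (Data Analysis) fits a mixed model to an unspecified outcome and looks at the group-by-time interaction. Its one multiplicity sentence adjusts pairwise comparisons of group slopes.

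**What is sized.** The synopsis sizes on CD34+/KDR+ cells. Section 8 sizes on CD34+/KDR+ cells and on VEGF. Neither place calls either of them primary.

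**The concern.** A primary analysis needs one named outcome, or several with a rule for combining them. Here the primary label covers a whole laboratory panel, the significance level is shared without division, and the documents do not say whether one, some or all results must be positive. A single significant gene or assay could be reported as meeting the primary objective, and nothing in the plan would hold the error of that claim at 5%. The synopsis adds to the doubt, because a reader who starts there cannot tell which measure answers the primary question.

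**Working it through.** **1. Counting the primary outcomes (Section 6).**

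| Domain | Low count | High count |
|---|---|---|
| FACS populations | 3 (four listed, CD34/KDR twice) | 4 (adds total CD34+ count) |
| Colony-forming units | 1 | 1 |
| Migration | 1 (SDF-1 as one dose-response) | 3 (adds a second SDF-1 concentration and VEGF-A) |
| Tube formation | 0 | 1 |
| Genes | 19 (20 names; glutathione peroxidase appears again as GPX) | 19 |
| **Total** | **24** | **28** |

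The marker and gene lists are given as examples, so 28 is not a ceiling.

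**2. Does the multiplicity sentence help?** Two arms give 2×1/2 = 1 pairwise slope comparison per outcome. Adjusting one comparison changes nothing, and the sentence does not address comparisons across outcomes.

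**3. Error if any one positive outcome counted.** Assume all nulls are true and each outcome is tested two-sided at 0.05. Under independence the chance of at least one positive is 1 − 0.95^k:
- k = 24: 1 − 0.95^24 = 0.708, with 24 × 0.05 = 1.2 false positives expected.
- k = 28: 1 − 0.95^28 = 0.762, with 28 × 0.05 = 1.4 expected.

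The documents give no correlation between outcomes. Assuming a common correlation ρ among normal test statistics, and integrating numerically over the shared component:

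| Outcomes | ρ = 0 | ρ = 0.3 | ρ = 0.5 | ρ = 0.7 |
|---|---|---|---|---|
| 24 | 71% | 60% | 46% | 31% |
| 28 | 76% | 64% | 49% | 33% |

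**4. Does the existing sizing carry over to one named endpoint?** Inputs from Section 8 for CD34+/KDR+: slope difference 1 per week (4 against 5), SD 15, correlation 0.60 among repeated measures, visits at weeks 0, 6 and 12. The visit times have sum of squares Sxx = 36 + 0 + 36 = 72. With complete data the fitted slope is (Y12 − Y0)/12, so a slope test and a week 12 change contrast are the same comparison.

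SE = sqrt(2 × SD² × (1 − 0.60) / (n × 72)), and power = Φ(difference/SE − z). At n = 18, SE = sqrt(2 × 225 × 0.4 / 1296) = 0.3727 and difference/SE = 2.683. For the 20% effect at n = 20, SE = 0.3536 and difference/SE = 0.8/0.3536 = 2.263.

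| Case | Stated | One-sided 0.05, normal | Two-sided 0.05, normal |
|---|---|---|---|
| CD34+/KDR+, 25% effect, n = 18 | 84% | 85.0% | 76.5% |
| CD34+/KDR+, 25% effect, n = 22 | 90% | 90.7% | 84.3% |
| CD34+/KDR+, 20% effect, n = 18 | 70% | 69.2% | 57.4% |
| CD34+/KDR+, 20% effect, n = 20 | 73% | 73.2% | 61.9% |
| VEGF, n = 18 | 77% | 77.9% | 67.5% |
| VEGF, n = 27 | 90% | 90.5% | 84.1% |

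All six stated powers reproduce within 2 points for a single outcome tested one-sided, and none does two-sided. With the t distribution, the first row becomes 83.8% one-sided and 74.1% two-sided (34 df), and the fourth becomes 71.8% and 59.7% (38 df). Hence the two-sided ranges of 74-77% and 60-62%.

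**The case against.** The best defence is that the sizing points to CD34+/KDR+ as the lead outcome: it is the only one in the synopsis sizing and the first in Section 8. That makes it the natural choice, but sizing on a measure does not commit the trial to being judged on it. Section 8 also sizes on VEGF, speaks of study outcomes in the plural, and fits its model to a generic outcome.

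A reader might infer that the synopsis flatly contradicts Sections 2.1 and 6 by demoting the CD34+ measures. The documents do not support that. The secondary aim in the synopsis is to validate these measures as biomarkers, which is a different aim from testing a treatment effect, and one measure can serve both. Section 4.1 also equates endothelial function with the progenitor-cell measures, which could supply the missing primary measure. The synopsis is unclear, not contradictory.

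The count is soft, and that criticism stands. It depends on how concentrations and duplicates are treated. Tube formation is named once and is absent from the list of planned assays that follows. The low count leaves out total CD34+ number. Independence is also unlikely for 19 genes measured in the same cells. These points move the figures within the range shown; they do not supply a primary outcome.

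Reporting power for VEGF while serum VEGF-A is a secondary measure is not in itself an error.

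**Conclusion.** The point holds and must be fixed. The documents name no single primary outcome and state no success rule, and the plan has no error control across a primary panel of roughly 24 to 28 outcomes.

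It would be tempting to say that the plan carries a false-positive rate of 71-76%. It does not say enough for that. Those figures need independence, true nulls throughout, and an any-one-positive rule that appears nowhere; Section 4.1 reads more like an expectation that the measures improve together. With correlation 0.7 the same rule gives 31-33%, still about six times the nominal 5%. The firm conclusion is that the 5% level is not secured, with the size depending on a rule and a correlation that the documents leave open.

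The match to one-sided 0.05 is a separate matter. The documents do not state sidedness, so this is not proof that a one-sided test was intended. It means only that the stated powers cannot be carried over unchanged to a two-sided test.

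**What to change.** Before unblinding:

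1. Name CD34+/KDR+ cell number as the single primary endpoint. A fixed testing order or a co-primary rule would also cure the defect, but this choice matches the synopsis sizing.
2. Test it once, by a pre-specified group-by-time contrast from baseline to week 12 at two-sided 0.05. Fix the time coding and the covariates in advance. Section 8 now lets a linearity test choose the time coding and lets imbalance judged by inspection choose the covariates, so naming the outcome alone would still leave the test open.
3. Label the other FACS populations, colony-forming units, migration and gene expression secondary or exploratory.
4. Replace the pairwise-slopes sentence in Section 8 with this rule, and align the synopsis, Section 2.1 and Section 6 with it.

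As a separate edit, state the sidedness and restate the power without enrolling more: CD34+/KDR+ at 18 per group about 74-77% instead of 84%, and the synopsis case (20% effect, 20 per group) about 60-62% instead of 73%.

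The cost is wording only, with no change to visits, assays or recruitment. There are two real downsides: the other measures lose primary status, and the stated power becomes less favourable.

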1 INTRODUCTION

Type 2 diabetes is a national epidemic ^{1,2} with significant macro and microvascular complications³. Insulin resistance in prediabetes and early and late diabetes are associated with endothelial dysfunction⁴.

A few studies indicate that EPCs can act as a suitable bio-marker ⁵⁻⁷ for monitoring cardiovascular morbidity. In this proposal we suggest that EPCs or CD34 positive cells can act as a suitable cellular biomarker for estimating and following endothelial dysfunction in early type 2 diabetes patients.

EPCs have been used as a regenerative tool in ischemic myocardium and diabetic wound healing ⁸⁻¹³. Endothelial dysfunction with associated inflammation may be a consequence of excess super-oxide presence in a setting of diabetes which is a pro-oxidative stress condition causing EPC dysfunction and senescence¹⁴. Therefore monitoring EPC number, function and gene expression may serve as a very useful cellular bio-marker for cardiovascular complications in early type 2 diabetes.

Though lifestyle modification has been proposed as a main stay for prevention and treatment of early type 2 diabetes, ^{2, 15-19} several new therapies for diabetes have been developed in recent years². Incretins and incretin mimetics appear to hold promise. Oral DPP-4 inhibitors have been shown to increase EPCs in patients with type 2 diabetes ²⁰ reportedly via SDF-1 alpha up-regulation. Interestingly, up-regulation of SDF-1 alpha and vascular endothelial growth factor (VEGF), both chemotactic factors increase mobilization and recruitment of EPCs in the face of acute ischemic injury for repair and regeneration.²¹⁻²⁴.

Several studies have shown positive effect of incretins (Glucagon like peptide, GLP-1) and incretin receptor agonists (GLP-1 receptor agonists) on cardiovascular risk factors in type 2 diabetes patients^{20,25} and even in patients with chronic heart failure and left ventricular dysfunction who do not have diabetes^{26,27}.

DPP-4 Inhibitors may have cardio-protective effects of their own, as they increase bio-availability of endogenous GLP-1. They improve blood flow and nitric oxide production in endothelium^{28, 29}. These are unique properties not demonstrated by other oral diabetes medications ²⁸. The mechanism underlying these effects may be mediated by increased nitric oxide bioavailability but is not completely known. It is possible that Saxagliptin, a member of DPP-4 inhibitor group of drugs may be able to improve number and function

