of CD34+ endothelial progenitor cells by up-regulating chemotactic agent SDF1 alpha (DPP-4 degrades SDF-1) and its receptor CXCR4^{7, 20, 21, 30, 31}.

Poor viability and function of EPCs in early diabetes may ultimately affect the repair and regeneration of the endothelium and prompt intervention may reduce or reverse cardiovascular risk by improving EPC survival and function above and beyond adequate glucose metabolism control.

Therefore we would like to explore the effect of Saxagliptin in addition to lifestyle intervention, on number and function and gene expression of EPC and impact on endothelial dysfunction in type 2 diabetes.

This proposed study will recruit patients with type 2 diabetes of less than 8 years duration, who are already on Metformin (≥ 1.0 to ≤ 2 gm/d, stable dose for at least 3 months) but still remain poorly controlled with HbA1C between 6% and 9% (both values inclusive), but not overtly out of control ($> 9\%$ of HbA1C). In these patients we seek to compare the effect of saxagliptin and lifestyle modification versus lifestyle modification and placebo on endothelial function, particularly the cellular end-point. Initially life-style intervention with diet and regular aerobic activity (as per Standards of Diabetes Care: Diabetes Care Supplement: Jan 2014) will be undertaken for 4 weeks. Subjects will begin taking 5.0 mg of Saxagliptin or placebo after initial 4 weeks of stabilization of life style modification and will be withdrawn from the study if the medication or placebo is not tolerated. We will use the maximum approved dose of saxagliptin in order to discern a definitive effect.

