1.1 Summary of Results of Investigational Program

1.1.1 Pharmacology of Saxagliptin

Saxagliptin has been shown to be a highly potent, reversible, competitive inhibitor of human DPP-4,⁶⁵ with a K_i value of 1.3 ± 0.3 nM (0.41ng/mL) at 37°C. The 5-hydroxyadamantyl metabolite of saxagliptin (5-hydroxysaxagliptin, BMS-510849), the major metabolite of saxagliptin both in vitro and in vivo in animals and humans, was also a competitive inhibitor of DPP-4 at 37°C, with a K_i value of 2.6 ± 1.0 nM (0.86 ng/mL. 2-fold less potent than saxagliptin).

The clinical pharmacology program consisted of 39 studies in 1090 subjects, 1037 of whom were dosed with saxagliptin. The Phase 2b and Phase 3 worldwide clinical development program in T2DM included 8 core studies in which 4607 subjects were randomized and treated. Of these, 3356 subjects received double-blind saxagliptin; an additional 66 subjects

received open-label saxagliptin 10 mg in CV181011. Over 1000 subjects have received saxagliptin for more than 76 weeks, including 260 who received saxagliptin 10 mg, and over 450 subjects have received saxagliptin for more than 102 weeks. In studies CV181011 and CV181014, 244 subjects have received saxagliptin for > 204 weeks.^{66,67}

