1.1.5 Clinical Efficacy of Saxagliptin

Saxagliptin Phase 2b and Phase 3 worldwide clinical development program in T2DM included eight studies in which over 4600 subjects combined with the results from clinical pharmacology studies support the oral dose of saxagliptin 5 mg once daily as the usual clinical dose in a wide range of subjects with T2DM, as either monotherapy, add-on combination therapy with metformin, a thiazolidinedione (TZD), or a sulfonylurea (SU), or initial combination therapy with metformin.

In the Phase 2b dose-ranging study, administration of saxagliptin 5 mg was associated with significant inhibition of plasma DPP-4 activity at the trough of the dosing interval as well

as clinically meaningful decreases in A1C, fasting plasma glucose (FPG), and postprandial serum glucose. The results from the short-term periods of the Phase 3 studies confirmed clinically meaningful benefits of saxagliptin 5 mg on A1C, as well as FPG, postprandial glucose, insulin, C-peptide, and glucagon levels. In the monotherapy studies (CV181011 and CV181038), add-on combination therapy studies (CV181014, CV181013, CV181040 with metformin, TZD, glyburide, respectively), and initial combination study with metformin (CV181039), treatment with saxagliptin produced statistically significant reductions in A1C relative to control. A greater percentage of subjects treated with saxagliptin achieved target glycemic goals including A1C levels < 7% compared with subjects treated with placebo or active comparator. The saxagliptin 5 mg groups achieved greater reductions from baseline in A1C than the saxagliptin 2.5 mg groups in five of the six core Phase 3 studies (one of the core studies, Study CV181039, did not have a 2.5 mg treatment group). There was no consistent evidence for an incremental efficacy benefit for 10 mg beyond that seen for the 5 mg dose.

Saxagliptin treatment consistently demonstrated a beneficial antihyperglycemic effect across subgroups of demographic and baseline diabetes characteristics.

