4 INVESTIGATIONAL PLAN

4.1 Study Design and Duration

Study Schema, 42 Type 2 diabetic Subjects Aged 40-70 on stable dose of Metformin

+/- 3 days for visits Wk 0 Wk 6 and Wk 12, if the particular day is not feasible

*Assessed at week 0, 6 and 12: Biochemical and cellular markers of endothelial function and Pulse wave analysis and velocity (PWA and PWV).

Available related studies and Expected Results: Studies measuring changes to EPCs in type 2 diabetes patients are very limited. To the best of our knowledge there are no studies examining the effect of saxagliptin in early diabetes on patient's CD34/KDR+ve cells and comparing that to the effect of lifestyle + metformin on CD34+ve cell population. The regenerative potential of EPC is thought to be due to direct incorporation into vascular endothelium and/or the secretion of angio-supportive factors to enhance endothelial repair and function^{17, 18, 19}. Our studies and others^{11, 12, 34}, have shown that various disease states, including those seen in diabetes, can deplete and damage EPC, thereby diminishing their regenerative potential. The inability to maintain or repair damaged endothelial tissue leads to cumulative vascular dysfunction and cardiovascular disease.

We hypothesize that monitoring *number, function and gene expression of endothelial progenitors will allow us to quantify cardiovascular disease risk at the onset and regenerative potential post intervention at a cellular level. It will also help us to identify and correlate the best endothelial function bio-chemical inflammatory marker as an early indicator of cardiovascular disease progression in early type 2 diabetes.*

Therefore, studying the effects of Saxagliptin which can increase SDF1 alpha levels and possibly CXCR4 receptor expression as an intervention on the number and health of EPCs may not only provide insight on the biological role of these cells, but they can be used as a tool to study vascular biology and lastly can be a potential target for prevention of diabetes vascular complications.

We expect to establish that saxagliptin improves endothelial function that is EPC number, function, gene expression and bio-inflammatory markers beyond its glycemic control effect in type 2 diabetes patients.

Saxagliptin 5 mg or placebo will be added to patients who have type 2 diabetes diagnosed less than 8 years with HbA1C of 6 to 9 % (both inclusive) while being on lifestyle modification and Metformin (≥ 1.0 to ≤ 2 gm/d orally).

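### SDF-1alpha and GLP-1 are assayed in serum with no described step to stop DPP-4 after the draw, so loss in the tube could mimic part or all of a between-arm rise

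*Combined protocol and SAP*

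**What the plan says.** The Secondary Measures list, in the methods text that follows Section 6.2, includes this line: "Serum SOD activity and SDF1 alpha (ELISA), VEGF-A (ELISA) and GLP-1 (ELISA) levels will also be assessed". The volume paragraph under that list divides the 85 mL drawn per visit into 60 mL for CD34+ cell work and "25 mL for biochemistry and serum ELISA assays". Serum is therefore named twice, and the second mention covers the ELISAs as a group.

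Other sections bear on the same two analytes:

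- The Introduction proposes that saxagliptin acts by "up-regulating chemotactic agent SDF1 alpha (DPP-4 degrades SDF-1) and its receptor CXCR4". It also says DPP-4 inhibitors may protect the heart "as they increase bio-availability of endogenous GLP-1".
- Section 4.1 gives the expected direction: "studying the effects of Saxagliptin which can increase SDF1 alpha levels and possibly CXCR4 receptor expression".
- Section 1.1.1 describes the drug as a "highly potent, reversible, competitive inhibitor of human DPP-4".
- Section 1.1.5 says the 5 mg dose produced "significant inhibition of plasma DPP-4 activity at the trough of the dosing interval", without a percentage.
- Section 8, Data Analysis, makes the group-by-time interaction in a linear mixed model the comparison of interest, with measurements at weeks 0, 6 and 12.

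The text mentions no enzyme inhibitor in the tube, chilling, time to separation or time to freezing for these assays. It does not say whether they read the uncleaved (intact) peptide or all peptide whether or not it has been cleaved (total).

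**The concern.** Serum has to stand and clot before it is separated, and DPP-4 is present while it does. If the assay reads intact peptide, whatever the enzyme cleaves in that interval is lost from the result. A saxagliptin patient's sample carries drug into the tube, and a placebo patient's does not. Treatment can therefore alter the measurement after the blood has left the patient, as well as the level inside the patient.

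Randomisation and masking do not remove this, because the assigned treatment itself causes the difference. Adjusting for the week 0 value does not remove it either, because no one is on study drug at week 0.

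At stake is the reading of the proposed mechanism. A rise in circulating SDF-1alpha is the route by which the protocol expects the drug to act on progenitor cells. A reader shown a group-by-time effect on serum SDF-1alpha could not tell how much arose in the patient and how much in the tube.

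**Working it through.** **Step 1: does the pattern match the tested contrast?**

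| Visit | Placebo sample | Saxagliptin sample |
|---|---|---|
| Week 0 (before study drug) | enzyme active in tube | enzyme active in tube |
| Weeks 6 and 12 | enzyme active in tube | enzyme at least partly inhibited in tube |

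The week 6 and 12 entries for saxagliptin rest on Section 1.1.5: inhibition persists at trough, so it is present even if the morning dose has not been taken before a fasting visit. The difference between arms appears only after week 0. If it is a constant amount a at both later visits, the least-squares slope over times 0, 6, 12 (mean 6, sum of squares 72) is (-6 x 0 + 0 x a + 6 x a)/72 = a/12 per week. That enters the group-by-time coefficient directly, in the direction of the expected SDF-1alpha rise.

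**Step 2: how large could it be?**

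The plan gives no effect size, SD or power for SDF-1alpha or GLP-1, so there is no stated figure to reproduce. It also gives no rate of loss in a tube. Both inputs below are assumptions:

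- d = share of intact peptide lost in a placebo tube before separation, 0 to 50%
- i = share of that loss blocked by drug in a saxagliptin tube, 50 to 90%

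With no true effect in the patient, the apparent saxagliptin/placebo ratio of levels is:

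- Proportional model: (1 - (1 - i)d)/(1 - d)
- First-order decay: (1 - d)^(-i)

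| d | Proportional, i = 0.5 to 0.9 | First-order, i = 0.5 to 0.9 |
|---|---|---|
| 0% | 1.000 | 1.000 |
| 10% | 1.056 to 1.100 | 1.054 to 1.099 |
| 20% | 1.125 to 1.225 | 1.118 to 1.222 |
| 30% | 1.214 to 1.386 | 1.195 to 1.379 |
| 50% | 1.500 to 1.900 | 1.414 to 1.866 |

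For example, at d = 30% and i = 0.5 the proportional model gives (1 - 0.15)/0.70 = 1.214. With a total-form assay the ratio stays at about 1.00 for any d.

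**Step 3: what would an artefact do to the test?**

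I borrow the plan's slope-comparison approach from Section 8, with 18 completers per group and correlation 0.60. As a check on the formula, for CD34+/KDR+ cells (slope difference 1 per week, SD 15) the standard error is sqrt(2 x 225 x 0.40/(18 x 72)) = 0.373. One-sided 0.05 then gives power 0.850 against the stated 0.84 (two-sided gives 0.765).

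For a marker in SD units, the standard error is sqrt(2 x 0.40/(18 x 72)) = 0.0248 per week. An artefact of a SD gives z = (a/12)/0.0248. At two-sided 0.05, with no true effect, the chance of a significant interaction for that marker is:

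| Artefact at week 12 | Chance of a false positive |
|---|---|
| 0 | 5% |
| 0.2 SD | 10% |
| 0.3 SD | 17% |
| 0.5 SD | 39% |

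The ratios in Step 2 cannot be converted into these SD units, because the documents give no SD for either marker. The correlation and group size are those used to size other outcomes.

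**The case against.** The strongest reply is that this is an unspecified handling step and no bias has been shown. A false rise needs three things together: an assay that reads intact peptide, material loss before separation, and no inhibitor or rapid cooling. The protocol settles none of them. Tube type and spin time often sit in a laboratory manual, and silence here does not prove that the tubes are untreated. All of this stands. A reader might infer that a false between-arm rise is bound to occur; the documents do not support that.

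A reader might also infer that saxagliptin samples are fully protected. Section 1.1.1 calls the inhibition reversible and competitive, and Section 1.1.5 gives no percentage, so only a partial contrast can be assumed.

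It would be tempting to set the ratios above beside the 25% and 50% effects in the sample-size table. That comparison fails: those are ratios of weekly slopes (4 against 5 cells, 0.6 against 0.9 pg/mL) for CD34+/KDR+ cells and VEGF, whereas the ratios here are of concentration levels for other analytes.

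Finally, the reach is limited. SDF-1alpha and GLP-1 levels are not named in the secondary objectives of Section 2.2 and were not used to size the trial. The mechanism is also examined through CXCR4 by FACS, SDF-1 and CXCR4 gene expression in CD34+ cells, and the migration assay, none of which depends on peptide surviving in a serum tube. These do not replace a circulating SDF-1alpha level, but the mechanistic argument does not rest on this ELISA alone.

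The reply does not remove the core. The plan does choose a matrix, serum, for two analytes tied to the enzyme that one arm's drug inhibits. It describes no control of that enzyme after the draw, although the cell assays are specified down to plate size, pore size and a catalogue number.

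**Conclusion.** The point holds in a conditional form. As written, the plan cannot separate a rise in the patient from less loss in the tube for SDF-1alpha and GLP-1, and any artefact would fall into the group-by-time term in the hypothesised direction.

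- If the assays read intact peptide, part or all of an observed rise could be due to handling. On the assumed ranges (0-50% loss, 50-90% of it blocked) the spurious level ratio runs from 1.0 to about 1.9. The lower end is no artefact, and nothing in the documents says where in the range the trial would fall.
- If they read total peptide, the artefact is largely absent. The measurement then misses protection from degradation, which is part of the stated rationale ("DPP-4 degrades SDF-1"), and shows only a change in total peptide.

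The primary measures (CD34+ cell number, function and gene expression) are not affected. A reader might infer that all serum already collected is worthless; that goes too far, because it depends on the assay form and on how quickly samples were processed. The fault lies in two secondary markers and is cheap to correct, so it should be corrected.

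**What to change.** In the Secondary Measures text after Section 6.2:

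- For SDF-1alpha and GLP-1 only, replace serum with plasma from chilled tubes containing a DPP-4 inhibitor, in all subjects of both arms at weeks 0, 6 and 12.
- State a fixed maximum time to separation and to freezing, the same for every sample.
- Name the peptide form each assay reads. Intact is the form that shows protection from degradation; report total alongside it if feasible.
- Do not mix matrices within a subject: a serum week 0 value should not serve as baseline for plasma follow-up values.
- For samples already collected as serum without inhibitor, do not interpret an intact-form between-arm difference as an effect in the patient unless laboratory records of assay form and processing time support it.

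Cost: different tubes for part of the 25 mL already drawn, slightly more sample handling, and the price of a second assay if total is added. No extra visit or blood volume is needed.
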